1 BACKGROUND INFORMATION AND RATIONALE

1.1 Introduction

Acute myeloid leukemia (AML) is the second most common pediatric hematologic malignancy with approximately 600 new cases per year among patients under 20 years of age. Although AML accounts for only about 20% of leukemias in children, it is responsible for more than half of pediatric leukemia deaths (1).

All pediatric patients with newly diagnosed AML receive multiple consecutive courses of intensive myelosuppressive chemotherapy aimed to attain complete remission (induction) and to prevent relapse (intensification) (2). Each regimen is followed by a period of prolonged severe neutropenia during which patients are at high risk for infection and hemorrhage. Previous reports have found that 57-80% of febrile neutropenia episodes among pediatric AML patients are compromised by at least one microbiologically documented infection (3, 4) with bacteremia constituting the most prevalent infection (5). These infectious complications remain a major cause of therapy-associated morbidity and mortality in children with AML (6, 7).

Recently published pediatric neutropenia guidelines make no specific recommendations regarding discharge from hospital after chemotherapy for AML because "there are no validated schemas for defining those patients at high-risk of developing complications of fever and neutropenia" (8). As a result, clinicians are left to decide whether to keep a child in the hospital until the neutropenia resolves (on average 35 days) or discharge a child to outpatient management within a few days of chemotherapy completion with instructions to return if symptoms of infection develop. Physicians that elect to observe patients with neutropenia in the hospital do so under the assumption that hospital observation will reduce the risk of serious infection and thereby reduce delays in starting the next course of chemotherapy. There is documented variation in practice across Children's Oncology Group (COG) institutions on inpatient versus outpatient management of neutropenia with approximately 60% of COG institutions reporting a policy to always keep patients hospitalized during severely neutropenic periods and the remaining 40% of hospitals reporting a policy of home management some or all of the time (9, 10). This variation in practice highlights the need for additional data on clinician-centered outcomes to appropriately guide the management of neutropenia in pediatric AML patients.

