3.3.2 Total Number of Study Sites/Total Number of Subjects Projected

Chart abstraction will be conducted at the following seventeen US investigative sites: Ann Arbor (*C.S. Mott Children's Hospital*), Atlanta (*Children's Healthcare of Atlanta*), Chicago (*Ann & Robert H Lurie Children's Hospital of Chicago*), Dallas (*Children's Medical Center of Dallas – University of Texas Southwestern Medical Center*), Detroit (*Children's Hospital of Michigan*), Houston (*Texas Children's Hospital*), Jackson (*Children's of Mississippi*), Little Rock (*Arkansas Children's Hospital*), New Orleans (*Ochsner Medical Center for Children*), Palo Alto (*Lucile Packard Children's Hospital Stanford*), Philadelphia (*Children's Hospital of Philadelphia*), Salt Lake City (*Primary Children's Medical Center*), San Diego (*Rady Children's Hospital*), Seattle (*Seattle Children's Hospital*), Denver (*Children's Hospital of Colorado*), Nemours/A.I. duPont Hospital for Children, and DFCI/Boston Children's Hospital (*Boston, MA*). These sites were chosen based on geographic location, their substantial AML/MDS patient volume, and the variation in primary strategy of neutropenia management (inpatient versus outpatient).

We expect to identify a total of approximately 600 newly diagnosed AML patients across the seventeen participating institutions over the study period of which approximately 540 are expected to meet early discharge eligibility criteria.

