6.2 Control of Bias and Confounding

This is an observational cohort study, so subjects are not assigned by a process of randomization and are therefore subject to bias. However, analyses of our data will control for potential confounding by various patient- and hospital- level factors. Additionally, there is a possibility of exposure misclassification given that patients who are discharged more than 3 days after chemotherapy completion but well before neutropenia recovery will still be included in the inpatient management group. To account for this imperfect specificity, sensitivity analyses will be performed utilizing a less strict threshold for discharge classification (e.g., 5- or 10 days post-chemotherapy).

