6.3 Statistical Methods

6.3.1 Analysis of Primary Outcomes of Interest

Propensity score analyses will be used to adjust for potential confounding by baseline covariates. First, bivariate analyses will be performed to evaluate relationships between each baseline covariate and neutropenia management strategy as well as each outcome of interest. Next, propensity scores will be derived from the predicted probabilities estimated from logistic regression models of the use of outpatient versus inpatient management during neutropenia conditional on all baseline factors determined to be true confounders (i.e., those associated with both exposure and outcome) and those determined to be potential confounders (i.e., those associated only with the outcome interests). Patients will then be stratified into five groups using quintiles of the estimated propensity score. The distributions of exposure within the quintiles will be examined for sufficient sample sizes and balance. Within each stratum, the patients managed as outpatient and those managed as inpatient will ideally have similar values of the propensity score and likewise the distribution of measured baseline covariates will be comparable between them.

Log-binomial regression will be used to estimate risk ratios with 95% confidence intervals (CI) comparing the incidence of bacteremia following outpatient versus inpatient neutropenia management strategy. Control for confounding will be accomplished through adjustment for propensity score by quintiles as well as any remaining unbalanced patient- or hospital-level confounders.

Generalized linear regression models will be utilized to compare time (in days) from three days after completion of one chemotherapy course to initiation of the next course of chemotherapy by neutropenia management strategy (outpatient versus inpatient). Before model fitting, the normality of the outcome will be assessed. If the normality assumption holds, then traditional linear models (normal distribution with an identity link) will be utilized. If the distribution of time to next course is significantly skewed, then models assuming a gamma or log-normal distribution as appropriate will be used. Again, control for confounding will be accomplished through adjustment for propensity score by quintiles as well as any remaining unbalanced confounders.

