6.4 Sample Size and Power

Assuming 100% capture of eligible patients (waivers of consent obtained from all participating sites), we expect to identify a total of 600 newly diagnosed AML/MDS patients across the seventeen participating centers. Assuming 90% of identified patients will be early discharge eligible, the anticipated study population will be 540 patients. Based on the rates for the individual participating sites, approximately 27% of the study population will be managed as outpatients (n=146) and the remaining will be managed as inpatients (n=394) during neutropenia. Assuming a baseline risk of bacteremia of 60%, the proposed size of the two study arms would provide greater than 80% power to detect a 13% difference in bacteremia rates among patients managed as outpatients versus those that remain hospitalized, with a significance level of 0.05. A 13% difference in bacteremia rates would also be a clinically significant difference. For time to next chemotherapy course, we used a two sample t-test in the power calculation to be conservative (i.e., statistical analysis using a generalized linear model with correct distribution will result in creased power over a t-test). Assuming each patient contributes one treatment course and an average time to next chemotherapy course of 29 days and a standard deviation (SD) of 10 (based on preliminary data), our study will have 85.0% power to detect a difference of 3 days between the two groups, with a significance level of 0.05.

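### Management strategy is likely to be partly clustered by hospital, but neither primary model states a hospital effect or clustered variance: if within-hospital outcome correlation remains after adjustment, the intervals are too narrow and the stated power may be too high

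*Combined protocol and SAP*

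**What the plan says.** Section 3.3.2 lists 17 hospitals and gives, as one reason for choosing them, "the variation in primary strategy of neutropenia management (inpatient versus outpatient". Section 6.4 takes the exposure split from site figures: "Based on the rates for the individual participating sites, approximately 27% of the study population will be managed as outpatients (n=146", with the other 394 as inpatients. Section 1.1 describes differing institutional policies, with about 60% of institutions always keeping patients in hospital and "the remaining 40% of hospitals reporting a policy of home management some or all of the time". That statement is about Children's Oncology Group institutions in general, not these 17.

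On analysis, section 6.2 promises that "analyses of our data will control for potential confounding by various patient- and hospital- level factors". Section 6.3.1 specifies "Log-binomial regression will be used to estimate risk ratios with 95% confidence intervals (CI) comparing the incidence of bacteremia", with "adjustment for propensity score by quintiles as well as any remaining unbalanced patient- or hospital-level confounders". For the second endpoint it says "Generalized linear regression models will be utilized to compare time (in days) from three days after completion of one chemotherapy course" to the start of the next, adjusted for propensity quintiles and any remaining unbalanced confounders; hospital-level ones are not named there. For neither endpoint does it state a hospital fixed or random effect, estimating equations, a cluster-robust variance or an ICC. Mixed models appear only for the secondary cardiac-function outcome.

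On power, section 6.4 states that "the proposed size of the two study arms would provide greater than 80% power to detect a 13% difference in bacteremia rates", and gives 85.0% power for a 3-day difference from a two-sample t-test with one course per patient. Neither calculation mentions a design effect.

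**The concern.** An ordinary regression standard error treats patients as independent. It understates the uncertainty of the outpatient-versus-inpatient contrast when two things hold together: exposure is clustered by hospital, and outcomes within a hospital remain correlated after covariate adjustment. If exposure were spread evenly over hospitals, outcome correlation would do this contrast little harm.

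The first condition is likely here to some degree, given how sites were selected and where the 27% comes from. The second is plausible, because hospitals can differ in unmeasured practice that affects infection or the timing of the next course. Adjusting for measured hospital factors may shrink the remaining correlation, but nothing in the plan keeps the intervals valid if some is left. At stake are the coverage of the intervals behind both primary conclusions, and whether 540 patients carry as much information as section 6.4 assumes.

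The models also do not say whether the unit is the patient or the course. Any rule on clustering needs that answer.

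**Working it through.** **Inputs from section 6.4.** 146 outpatients and 394 inpatients (540 in all), 17 hospitals, baseline bacteremia risk 60%, difference 13%, SD 10 days, difference 3 days, significance level 0.05 (taken as two-sided). Not given: ICCs, site sizes, site outpatient rates, the formula for bacteremia power and the direction of the difference.

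**Step 1: reproduce the stated power under independence.** Take 60% vs 73%.
- Pooled risk = (394×0.60 + 146×0.73)/540 = 0.635.
- Null SE = √[0.635×0.365×(1/394 + 1/146)] = 0.0466.
- Alternative SE = √(0.60×0.40/394 + 0.73×0.27/146) = 0.0443.
- Pooled power = Φ[(0.13 − 1.96×0.0466)/0.0443] = 80.8%.
- Unpooled power = Φ(0.13/0.0443 − 1.96) = 83.6%.

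Both agree with the stated figure of more than 80%. For 60% vs 47% the pooled result is 77.2%, so the upward direction is used below.

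For time, the noncentrality is 3/[10×√(1/394 + 1/146)] = 3.10. With 538 degrees of freedom this gives 87.1%, about 2 points above the stated 85.0%.

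**Step 2: add hospital correlation (assumed values).** Mean hospital size m = 540/17 = 31.8, taken as equal across sites. Design effect DE = 1 + (m − 1) × exposure ICC × residual outcome ICC. The true SE is √DE times the unclustered one. Type I error of the unclustered test = 2×[1 − Φ(1.96/√DE)]. Power is recomputed with both arms divided by DE. This grid assumes one course per patient and no effective hospital adjustment.

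| Exposure ICC | Residual outcome ICC | DE | Type I error | Bacteremia power, pooled / unpooled | 3-day power |
|---|---|---|---|---|---|
| 0.2 | 0.01 | 1.06 | 5.7% | 78% / 81% | 85% |
| 0.2 | 0.02 | 1.12 | 6.4% | 76% / 79% | 83% |
| 0.2 | 0.05 | 1.31 | 8.7% | 69% / 73% | 77% |
| 0.5 | 0.01 | 1.15 | 6.8% | 75% / 78% | 82% |
| 0.5 | 0.02 | 1.31 | 8.7% | 69% / 73% | 77% |
| 0.5 | 0.05 | 1.77 | 14.1% | 56% / 60% | 64% |

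Nominal 95% coverage is 100% minus the type I error, so 94.3% down to 85.9%.

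**Step 3: where the stated figures fail.** Bacteremia power falls below 80% at DE of about 1.02 (pooled) or 1.10 (unpooled). Time power falls below 85.0% at DE of about 1.064. In the mildest row DE is 1.062, which gives 81.3% (unpooled) and 85.1% (time): both stated figures survive there.

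**Step 4: a check closer to the plan.** Null data were simulated for 17 hospitals of 32 patients, with 60% risk and 27% outpatient, 4,000 data sets per setting (Monte Carlo SE 0.3 to 0.6 points). The model was log-binomial with propensity quintiles and one measured hospital covariate. Residual outcome ICCs were 0 / 0.01 / 0.02 / 0.05.
- Exposure ICC about 0.5: model-based type I error 5.9 / 8.2 / 9.9 / 14.7%; delete-one-hospital jackknife with a t reference 5.2 / 5.9 / 5.6 / 5.5%.
- Exposure ICC about 0.2: model-based 6.0 / 6.0 / 7.2 / 9.6%; jackknife 5.5 / 5.0 / 5.7 / 6.4%.

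The model-based figures should be read against the roughly 6% seen with no residual correlation.

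**The case against.** The strongest reply is that the plan does address hospitals. Sections 6.2 and 6.3.1 commit to controlling hospital-level factors, and the wording does not rule out using hospital itself as an adjustment variable. With hospital indicators in the simulated model (fitted as a linear probability model), type I error was 4.6 to 5.5%, so the interval problem largely disappears. This stands as a possibility. But hospital indicators are not stated, and adjusting for measured imbalances is not the same as a hospital effect or a clustered variance.

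Second, at modest clustering the effect is small. With exposure ICC about 0.2 and residual outcome ICC 0.01, the simulation shows no increase over its own baseline. The large figures need an exposure ICC of about 0.5 together with a residual outcome ICC of 0.05, and neither is documented. This stands: the grid is a range of assumptions, not an estimate for this study.

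Third, if several courses per patient are analysed, information could exceed that of 540 single courses and offset some of the loss, less whatever within-patient correlation takes back. This also stands, because the unit is not stated.

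A reader might infer that the stated power is simply too high. The documents do not support that: both stated figures can hold in the mildest case above. A reader might also infer that the plan states a 95% interval for both endpoints. It does so only for the risk ratio; for time, an interval is implied by the model.

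**Conclusion.** The concern holds in conditional form. The omission is certain: no hospital effect or clustered variance is stated for either primary model, and the power rests on independent patients. The consequence needs both exposure clustering by hospital, which the documents make likely without giving its strength, and outcome correlation left after adjustment, which they do not address.

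Given both, the intervals are too narrow by a factor √DE, which is 1.03 to 1.33 over the assumed range, and the stated power may be too high. The size for this study cannot be established from the documents, and hospital covariates that explain more of the between-site variation would make it smaller. Bacteremia power has little slack on the pooled formula, where a product of the two ICCs above about 0.0007 takes it below 80%. Time power has more: its stated figure is exceeded only when the product passes about 0.002. The point should be fixed before analysis.

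**What to change.** In section 6.3.1:
- State the unit of analysis: one specified course per patient, or all eligible courses. If several courses per patient enter, say how within-patient correlation is handled.
- Require both primary contrasts to use variance clustered on hospital with a small-sample correction for 17 clusters, for example a delete-one-hospital jackknife or a bias-corrected sandwich variance with a t reference.
- Hospital fixed effects or stratification may be added as a sensitivity analysis where strategy varies within hospital. This also addresses confounding between hospitals, which clustered variance does not.

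In section 6.4, say that the stated power assumes independent patients, and show it over an assumed range of ICCs.

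The cost is SAP wording and standard software, with no new data or patients. The downside is somewhat wider intervals, less favourable stated power and few degrees of freedom with 17 hospitals. Fixed effects cost more, since they use only within-hospital variation. Multiplying both arms by (1 − exposure ICC), at exposure ICC 0.2 and 0.5, gives approximate power of 71% and 50% for bacteremia (60% vs 73%, pooled) and 79% and 59% for 3 days. Intervals are 1/√0.8 = 1.12 and 1/√0.5 = 1.41 times as wide as under independence. That is why they suit a sensitivity analysis better than the primary one.

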5 STUDY EVALUATIONS AND MEASUREMENTS

5.1 Screening and Monitoring Evaluations and Measurements

5.1.1 Medical Record Review

The following variables will be abstracted from the medical chart:

Variable Date of birth Sex Patient race/ethnicity Date of AML/MDS diagnosis Age at AML/MDS diagnosis Vital status Date of death or date of last known follow-up Location of death (in hospital or at home) AML subtype AML risk classification and cytogenetics Hospital admission start/stop dates Chemotherapy course Chemotherapy regimen and start/stop dates Course start/stop dates Clinical trial enrollment and specific protocol Documentation of deviation from planned chemotherapy course Presence/type of central line MRD post courses and dates of MRD obtained Post course remission status Daily max. fever; how was temperature taken Infections during chemotherapy courses ICU care during chemotherapy courses ANC measurements post chemotherapy Dates of ANC measurements Dates and results of microbiological cultures/PCRs onset during post chemotherapy course follow-up Mucositis by course Systematic antimicrobial prophylaxis at each course Height, weight, and body surface area at start of chemotherapy course Nutritional status/supplemental support requirements on day of chemotherapy completion Ability to practice oral hygiene Insurance status at course start (private, self-pay, public, other) English spoken? Home address Availability of working telephone Automobile/taxi voucher requirements Date of relapse Site of relapse Date of transplant Type of transplant Echocardiographic evaluations (e.g., dates, resulting measurements, measurement mode) Blood pressure and heart rate at echocardiographic evaluations Dexrazoxane administration Malignant blast percentage

| Bone marrow malignant blast percent |
|---|
| Empiric/definitive anti-infective use |
| Preferred language |
| Treatment and positive blood cultures at outside hospital (y/n) |
| Down Syndrome diagnosis |
| CNS status at the end of each course |
| Outpatient encounters (e.g., clinic/day hospital, ED) |

Some information will be retained for all screened patients to document the reasons for ineligibility. Specifically, we will be retaining information on age, leukemia diagnosis, treatment course, and whether the patient received reduced intensity chemotherapy.

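### Endpoint 2 model: enter prespecified baseline predictors whether or not they look balanced, with an interval that respects site; the benefit depends on an R² the plan does not state

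*Combined protocol and SAP*

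**What the plan says.** Section 6.3.1 (Analysis of Primary Outcomes of Interest) builds a propensity score from two kinds of baseline factor: those related to both management strategy and outcome, and those related to the outcome only. Patients are then grouped by score quintile. For endpoint 2, time to next course, the outcome model adjusts by "adjustment for propensity score by quintiles as well as any remaining unbalanced confounders". No threshold for imbalance is given and no variance estimator is named. The model is normal with identity link, or gamma or log-normal if the outcome is skewed.

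Section 5.1.1 shows that candidate predictors are already abstracted, for example "Chemotherapy course Chemotherapy regimen and start/stop dates", along with risk classification. It gives no strength of association with either endpoint.

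Section 6.4 plans endpoint 2 with a two-sample t-test and credits no gain from covariates. It assumes one course per patient and "an average time to next chemotherapy course of 29 days and a standard deviation (SD) of 10 (based on preliminary data"), with "approximately 27% of the study population will be managed as outpatients (n=146) and the remaining will be managed as inpatients (n=394) during neutropenia". It concludes that "our study will have 85.0% power to detect a difference of 3 days between the two groups".

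Section 3.3.2 says sites were chosen partly because their main management strategies differ. Section 6.2 promises control for hospital-level factors, but no section says how correlation between patients of the same hospital will be handled.

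**The concern.** Putting a predictor in the score and putting it in the outcome model do different things. In the score, it is balanced between the groups, and this makes the estimated difference vary less from sample to sample. Its effect on the outcome nevertheless stays in the residual of a quintile-only model. The usual model SE is built from that residual and treats the score as known, so it misses the gain.

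Quintiles are also coarse. Within a quintile the two groups can still differ on a confounder, by too little to be flagged as unbalanced but enough to shift the estimate.

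At stake on a primary endpoint are an interval that does not match the estimator's real variability, some residual confounding, and a covariate list settled after seeing the data under a rule with no threshold.

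**Working it through.** **Plan's own figure.** Inputs from Section 6.4: 394 and 146 patients, difference 3 days, SD 10, alpha 0.05 (two-sided assumed; the plan does not say).

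- SE = 10 × √(1/394 + 1/146) = 0.969 days; 95% half-width 1.96 × 0.969 = 1.90 days.
- Normal approximation: Φ(3/0.969 − 1.96) = 87.2%. The exact t-test gives 87.1%.

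The stated 85.0% is about 2 points lower, on the cautious side. Endpoint 2 thus meets its planned power with no covariate adjustment.

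**How large the SE mismatch can be.** Let R² be the share of outcome variance explained by baseline predictors (not in the documents; assumed). With independent patients and little confounding, the quintile-only model reports roughly SD × √(1/n₁ + 1/n₂). The real sampling error is at best that value times √(1 − R²). The ratio of reported to real SE is then at most about 1/√(1 − R²): 1.05 at R² 0.10, 1.12 at 0.20, 1.20 at 0.30.

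**Simulation A.** 540 independent patients, about 27% outpatients, 3-day effect, SD 10, normal outcome, 3,000 runs per row, four outcome-only predictors in an estimated score. Quintiles only is compared with quintiles plus the predictors:

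| R² (assumed) | True SD of estimate | Mean reported SE | Coverage | Reported/true, quintiles only |
|---|---|---|---|---|
| 0.10 | 0.910 vs 0.909 | 0.971 vs 0.930 | 96.1% vs 95.5% | 0.971/0.910 = 1.07 |
| 0.20 | 0.888 vs 0.887 | 0.961 vs 0.876 | 96.3% vs 94.7% | 0.961/0.888 = 1.08 |
| 0.30 | 0.823 vs 0.821 | 0.953 vs 0.820 | 97.7% vs 95.3% | 0.953/0.823 = 1.16 |

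The first row includes noise. An SD from 3,000 runs has a relative error of about 1/√6000 = 1.3%, and in the same runs the unadjusted model, whose SE should be right, shows 0.972/0.949 = 1.02.

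**Simulation B.** Eight covariates, four of them confounders, score c-statistic 0.73. Reported against true: 1.02/1.01 = 1.01 at R² 0.10 and 0.98/0.88 = 1.11 at R² 0.30. Together, A and B give about 0-7% at R² 0.10 and 11-16% at R² 0.30.

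**Residual confounding.** Simulation A was repeated with one confounder (log odds ratio 0.7 per SD for exposure, 5% of outcome variance) added to outcome-only predictors with R² 0.20 or 0.30. The true effect is 3 days.

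| Model | Mean estimate, R² 0.20 | Mean estimate, R² 0.30 |
|---|---|---|
| Unadjusted | 4.421 | 4.432 |
| Quintiles only | 3.134 | 3.145 |
| Quintiles plus covariates | 2.985 | 2.996 |

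At R² 0.20, quintiles remove (1.421 − 0.134)/1.421 = 91% of the bias and leave 0.13 days. With four confounders, other runs left 0.15 to 0.32 days, reduced to under 0.03 by entering the covariates.

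**Ordinary robust SEs.** On the quintile-only model at R² 0.30, the heteroscedasticity-robust SE was 0.962 against a model SE of 0.956 and a true SD of 0.847. In a second set of runs it was 0.972 against 0.974 and 0.876. It does not repair the mismatch.

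**Site.** 540/17 = 31.8 patients per site. If management were constant within site and the intraclass correlation (ICC) were 0.01 (both assumed), the variance factor would be 1 + 30.8 × 0.01 = 1.31. That nearly cancels the overstatement at R² 0.30, (0.953/0.823)² = 1.34. Simulated coverage with 17 sites and R² 0.20, quintiles only against quintiles plus covariates:

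- Exposure strongly site-driven: 93.6% vs 92.5% (ICC 0.01), 91.7% vs 90.3% (0.02), 86.5% vs 83.4% (0.05).
- Exposure moderately site-driven: 94.1% vs 93.5% (ICC 0.02). At ICC 0.01 the planned interval stays slightly conservative at 95.9%.

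**The case against.** Most of the case on the other side stands, and it limits the point.

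- **A reader might infer that the plan loses precision.** It does not. Outcome-only factors are in the score, and the two estimators vary almost equally: (0.823/0.821)² = 1.005 at R² 0.30, or half a percent in patients. Squaring the ratio of reported SEs instead, (0.953/0.820)² = 1.35, looks like a large saving in patients but describes interval width only.
- **A reader might infer that strong predictors are being ignored.** Section 5.1.1 lists variables without any association. At R² 0.10 or below, the ideal reduction in half-width is about 5% or less.
- **A reader might infer that the planned interval is too wide.** That requires independent patients and a default model SE. The plan names no SE, sites were chosen for differing practice, and with modest clustering the interval is too narrow. Adding covariates without handling site then makes coverage slightly worse.
- **A reader might infer that power is at risk.** Section 6.4 uses the unadjusted SD and already exceeds its stated figure.

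The gamma and log-normal alternatives were not simulated.

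What does not stand is the conclusion that the covariates may therefore stay out. Clustering is a separate gap, and two errors in opposite directions give a correct interval only by chance. Residual confounding within quintiles remains whatever SE is used.

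**Conclusion.** The point holds as a low-cost improvement to endpoint 2. The planned estimate is about as precise as a covariate-adjusted one. With a default SE and independent patients, its reported SE is too large by about 0-7% at R² 0.10 and 11-16% at R² 0.30, and quintiles alone leave about 0.1-0.3 days of confounding against a 3-day target difference. Entering the covariates brings the reported SE into line with the true SD, gives coverage near 95%, and nearly removes the bias.

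These sizes rest on assumed R² values, assumed strengths of confounding and a normal outcome. The direction of the interval error in the real study is unknown until the plan says how site is handled: it is conservative only if clustering is negligible. Nothing here invalidates the planned analysis or its power statement. Endpoint 1 was not examined.

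**What to change.** In Section 6.3.1:

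1. State that the endpoint 2 model contains management strategy, the score quintiles and a named list of baseline covariates (course, regimen, risk classification and the other score covariates), whether or not they look balanced. Limit the list to variables fixed before the management decision, and group sparse regimen categories in advance.
2. Name the variance estimator and make it respect site: for example, a bootstrap that resamples sites and re-estimates the score each time, or a site term with SEs suited to clustered data. With only 17 sites, state the small-sample correction. Do not rely on ordinary heteroscedasticity-robust SEs with a quintile-only model.
3. Make both changes together, because the first alone can slightly worsen coverage when patients cluster by site.

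The cost is some SAP wording, a few lines of code and about 10 extra parameters in 540 observations. No new data are needed. The covariate list would also no longer depend on an undefined judgement of imbalance.
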